# 2. Glossary

CRF	Case Report Form
G6PD	Glucose-6-phosphate Dehydrogenase
DAT	Direct Antibody Test
НСР	Healthcare Professional
HDN	Haemolytic disease of the newborn
IVIG	Intravenous immunoglobulin
NICE	National Institute for Health and Care Excellence
NICU	Neonatal intensive care unit
PTx	Phototherapy
Postnatal	Inpatient ward providing primarily midwife-led postnatal care,
area	including eg postnatal wards, labour wards, maternity wards,
	birth centres, and transitional care units (but excluding neonatal
	units or paediatric wards)
REACH	Research Evaluation and Audit for Child Health
SBR	Serum Bilirubin
SCBU	Special Care Baby Unit
ТсВ	Transcutaneous Bilirubinometer
PPI	Patient and public involvement
PIS	Participant information sheet

# 4. Summary and synopsis

Short title	BiliNEST
Methodology	Prospective multicentre observational study utilising the London REACH (Research Evaluation and Audit for Child Health) Network
Objectives / aims	We aim to investigate whether there are disparities in the jaundice assessments for neonates of different skin tones in London through the following objectives:  Primary Objectives:  1. To assess the level of first bilirubin measurement in neonates of different skin tones and determine whether neonates with darker skin tones are being assessed for jaundice once they have reached a higher bilirubin level, as compared to lighter skinned neonates.  2. To evaluate the agreement between TcB and SBR measurements in neonates of different skin tones.  Secondary Objectives:  1. To investigate immediate management of neonates of different skin tones undergoing assessment for jaundice: length of admission, investigations and receipt of interventions including phototherapy and exchange transfusion.  2. To review the range of existing local guidelines on management of neonatal jaundice, examining inter-guideline variation and variation from national clinical practice guidelines and the extent of guideline adherence.  3. To collate opinions and experiences from a diverse population of parents and carers regarding their understanding of neonatal jaundice and its management, the impact of skin tone and/or ethnicity on jaundice assessment in neonates and the acceptability of the neonatal skin tone tool.
Number of participants	Number of participants  A minimum of 560 participants (an estimated 28 participants from each site) will be recruited in order to reach an appropriate total sample size for the quantitative data sections as detailed in Section 10.
	Much fewer participants will be required for the qualitative data objective, a small group will be included from those in the quantitative section.
	Study population
Inclusion and exclusion criteria	Participants will be recruited for the primary objectives (quantitative) data collection if they fulfil the following criteria:
	Inclusion criteria:

	
 
Neonates born at ≥ 34 weeks gestation, now between 0-14 days postnatal age
 
Inpatients on any ward providing postnatal care excluding the neonatal unit or paediatric ward
 
Undergoing first objective assessment of bilirubin level for any reason (i.e. targeted screening, suspected jaundice by healthcare professional, suspected jaundice by parent / carer, poor feeding, any other clinical indication)
 
Age of parent/ carer ≥18 years
 

	Exclusion criteria:
	Readmission from the community     Parent/carer opted out of the study     Any medical condition known to affect skin colour e.g. cyanotic heart disease or widespread skin condition
	Participants will be recruited for Secondary Objective 3 (qualitative) data collection (survey and / or focus groups or semi-structured interviews) if they fulfil the following criteria:
	Inclusion criteria:
	
 
Parent/carer of neonate eligible for inclusion into quantitative data collection section of study (even if they have opted out of quantitative data collection).
 
≥18 years of age
 

	Exclusion criteria:
	Has not provided consent for participation in the survey and / or focus groups or semi-structured interviews.
	A linear mixed model, with skin tone and confounders as fixed effects and hospital as a random effect will be used for Primary Objective 1. 6 will be used for Primary Objective 2. Sample size calculations and a detailed statistical analysis plan, including Secondary Objective 1 can be found in Section 10.
Statistical methodology and analysis	Data collected for Secondary Objective 2 consists of web-based survey responses regarding local practice from each site, as well as any available guidelines and relevant information leaflets. A narrative synthesis will be conducted of their content.
	A thematic content approach will be used to analyse qualitative data collected for Secondary Objective 3. Qualitative manuscripts will utilise the Consolidated criteria for reporting qualitative research (COREQ) checklist.
Study duration	The total anticipated time for the study is 18 months, of which approximately the first 9 months will include local site approval processes

and data collection, followed by a 9 month period of analysis and preparation for dissemination (see Gantt chart attached for further detail).

The expected project milestones are detailed as follows:

Milestone 1: Study protocol and documentation finalised and approvals in place.

Outputs: Parent/carer pre-study survey, parent/carer representatives, IRAS form, REC approval, sponsorship approval, local R&D approvals at participating sites.

Milestone 2: Trained study leads in place at each participating site. *Outputs*: Live and recorded training webinars on study methodology including data collection tool with log of training record.

Milestone 3: Data collection for clinical data.

*Outputs*: Local held study logs, completed pseudonymised data entry into REDCap data collection tool.

Milestone 4: Qualitative data collection.

*Outputs*: Survey responses and semi-structured interviews or focus groups.

Milestone 5: Data analysis.

*Outputs*: Statistically valid quantitative results. Descriptive summary and thematic analysis of qualitative findings.

Milestone 6: Study write-up and dissemination of findings.

Outputs: Publication of results in peer reviewed journals, presentation of results in regional and national conferences/meetings, dissemination of results to relevant patient groups and wider public.

#### 5. Introduction

# 5.1. Background

Jaundice is one of the most common conditions affecting newborns in the first weeks of life. The consequences of delayed recognition and treatment of jaundice can be devastating; kernicterus is an avoidable condition that causes lifelong neurodisability if hyperbilirubinaemia is not promptly treated. A 2020 UK-based study found that infants from Black, South Asian or other ethnic groups were at a disproportionate risk of developing this complication, making up 50% of all cases of kernicterus despite representing only 25% of live births. Another study based in the UK and Ireland in 2007 found an association between ethnic minority origin and severe hyperbilirubinaemia.

The recent NHS Race and Health Observatory review of neonatal assessment and practice in Black, Asian and minority ethnic newborns highlights the potential for bias in the assessment of jaundice in neonates with darker skin tones . It recommends several areas for further research, including a better understanding on the level at which jaundice is visible, particularly in darker skinned neonates, and further investigation into the level at which a transcutaneous bilirubinometer (TcB) reading should be followed up by a serum bilirubin (SBR). The report also highlights that ethnicity does not correlate well with neonatal skin tone .

The updated 2023 NICE guidance on neonatal jaundice assessment and management undertook a literature search for papers relating to use of TcB in babies of different skin tones . Only two studies were identified that compared the relationship of TcB and SBR measurements in neonates of multiple skin tones and/or ethnicities. Maya-Enero et al used the Neomar skin colour scale to compare TcB-SBR correlation in neonates of four different skin tone groups . The study found increased variance with darker skin tones. However, of a sample size of 1359, only 23 babies were in the darkest skin tone group. Furthermore, this was a single site study and multiple comparison points from the same participants were included in the analysis, limiting internal and external validity. A second study conducted by Starowicz et al included 201 mostly premature neonates. They found that TcB overestimated bilirubin and was less precise in non-caucasian babies. This study is limited by sample size and the lack of defined skin tone groups - the study instead relies on the broad ethnicity categories of caucasian vs non-caucasian.

### 5.2. Rationale

The recent NHS Race and Health Observatory review of neonatal assessment and practice in Black, Asian and minority ethnic newborns highlights the potential for bias in the assessment of jaundice in neonates with darker skin tones. While multiple factors are likely to contribute to this, the failure to effectively detect jaundice in darker skinned neonates may play a role. In clinical practice, visual assessment remains a common indication for further jaundice investigations (e.g. TcB or SBR). The relationship between neonatal skin tone and jaundice assessment and diagnosis needs to be further explored.

Our first primary objective is to assess the level of first bilirubin measurement in neonates of different skin tones. This will enable us to determine if neonates with darker skin tones are only being assessed for jaundice once they have reached a higher bilirubin level, compared to lighter skinned neonates.

The second primary objective is to evaluate the agreement between TcB and SBR measurements in neonates of different skin tones.

During protocol development, parents and carers of infants in a range of London boroughs were invited to complete a survey to explore the need for the study including an exploration of parental experiences and concerns related to jaundice assessment in the context of different ethnic and racial backgrounds. Survey results represented a wide range of self-identified ethnic backgrounds and a significant proportion felt that their baby's ethnicity impacted their jaundice assessment, with a variety of reason why this might have been. We have used the results to inform protocol development in a number of ways. For example, to formulate focus group and semi-structured interview themes. Parent representatives also agree that the rationale for our study is well founded and the answers to the questions we have posed, will be valuable in the improvement of care for babies and families of all backgrounds.

#### 5.3. Risks / benefits

This is an observational study whereby the majority of data collected is part of routine care, and is anticipated to be very low risk.

The aim of the study is to improve healthcare professional assessment of jaundice in babies of all skin tones, reducing race-related health inequalities. Our study may also provide preliminary data for larger national studies used to inform wider practice in the UK. This study will improve the knowledge gap around why darker skinned babies are at higher risk of severe jaundice and its consequences. In addition, the study will contribute to the evidence base around the utility of non-invasive diagnostic methods (transcutaneous bilirubinometry) for neonatal jaundice. These conclusions will indirectly be helpful to a wide community of families.

Anticipated risks centre around acceptability of the skin tone tool use and concerns raised by parents or carers. We have therefore incorporated patient and public involvement (PPI) from the study's inception, allowing these psychological and sociological aspects to be built-into the study design, and ensure maximal acceptability.

There is a risk of insensitive language use and subsequent parental distress when discussing babies' natural skin tones or colour and the use of the tool. To mitigate this we have conducted a pre-study parental survey where parents gave opinions on acceptable language use and the challenges they have faced when talking about their baby's skin colour with healthcare professionals. Our findings have been incorporated into the phrasing of our parent information sheet and will inform the training we give to those involved in data collection and the language used in the survey and focus groups/ semi-structured interviews.

In addition, a feedback form link will be included in the participant information sheet (PIS), provided when enrolling a baby in the study, which will allow parents and

carers to raise any negative experiences of their interaction with research staff. While responses are anonymous, these will be monitored in real-time, enabling us to respond rapidly by updating the training of the data collection staff.

Our preliminary survey has also helped ensure that language used in the PIS is clear and easily understandable, for all levels of literacy. It will be professionally translated into the languages most relevant to the study population and local site translation services will be used to aid discussions around the opt-out consent process for quantitative data collection as well as consenting for the parent survey and focus groups/ semi-structured interviews.

The risk of data breach will be minimised by entering pseudonymised data into an encrypted data collection tool (REDCap) with data held within QMUL with our data Safehaven. Data entered here will not be linked to any participant-identifiable information. Parent survey responses will also be held in the encrypted NHS Microsoft 365 Forms platform and no patient identifiable data will be collected. Parent focus group/ semi-structured interview transcripts will be securely stored and only accessible to study teams for thematic analysis.

If the study enrolment happens as planned, there should be no delay in receipt of standard of care. However, should there be a misunderstanding between the midwifery and medical staff, there is a very small risk routine care would be delayed. This will therefore be highlighted very clearly in study team training to minimise this risk and ensure any clinical need is prioritised over study enrolment.

There is a risk that given the unblinded nature of the study, health care professional (HCP) perception of need for jaundice testing would be affected. We do not anticipate the number of jaundice tests at each site to increase due to participation in the study. However, we appreciate that the presence of an ongoing study may change healthcare worker behaviour, to minimise this the full details of the study will only be discussed with local study leads, who will not be the healthcare workers identifying patients for investigation for jaundice on data collection days.

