#### Study processes during prospective data collection phase

Potentially eligible neonates will be identified by postnatal area healthcare professionals and REACH/BiliNEST local study team members will determine their eligibility. The research team at each site will consist of the local lead study team member and a number of additional data collectors who have undergone training, all of whom are paediatric resident doctors as part of the direct care team. These individuals will review whether or not these neonates meet the eligibility criteria, and approach the birthing parent to ask if they are happy to discuss a research study. The number of participants deemed ineligible and the reason for exclusion will be documented. The study process and opt-out consent model will be explained verbally, and patient information leaflets will be provided in English or in the most relevant language available.

Local data collectors will receive an SOP detailing the introductory conversation aims with parents / carers, in particular, to be clear that there will be no detrimental consequences to them or their child if they opt out. A filmed, scripted example of an introduction will be included, that uses sensitive, non-coercive language; the script of which has been vetted by our PPI group. In addition, all data collectors will have completed Good Clinical Practice training, which includes the principles of appropriately obtaining informed consent and will have attended a training session on study processes.

The data collected from the parent/carer is listed in Table 1. The only data collected from participant examination is skin tone / colour group. Neonates will undergo a visual inspection by local study team members within twelve hours of their first bilirubin measurement and then categorisation into one of the four skin colour groups. We recognise that babies may be naturally lighter or darker than those depicted in the skin tone tool groups. When this is the case, babies will be assigned to the group closest to their natural skin colour e.g. for a baby who has a skin colour darker than group 4, they will be included within group 4. All study team members will be trained in the use of the tool to ensure the use of acceptable language and to minimise inter-user variability.

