# 9. Study procedures

#### **Opt-out Consent (Primary Objectives and Secondary Objective 1):**

- An opt-out consent model will be used for the primary objectives. This means that all eligible participants will be enrolled unless either of the parents / carers actively opt out. However, agreement from one parent is sufficient if the second parent is not present.
- A verbal and written explanation of the study will be provided, explaining the study objectives, procedures, risks, and benefits alongside the opt-out consent model.
- The written information will be available in a range of languages appropriate to the local population for each site.
- If required, a professional translator will be used to translate all relevant information, either in person or telephonically.
- Parents will be given a minimum of 15 minutes to consider the information and to ask questions as required, before study data is collected. The PIS will contain details on how to contact the study team to opt-out at any later stage.
- If parents opt-out of inclusion in the study, there will be no impact on the routine care provided

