## **Screening and recruitment:**

- On data collection days, staff members carrying out jaundice assessments in relevant inpatient areas will be notified and asked to alert the research team when any neonates are undergoing their first TCB or SBR
- Standard clinical care will not be delayed for enrollment
- Identification of potential eligible babies will occur via a written identification table in postnatal areas. Outcomes, i.e. included or excluded, and reasons for exclusion will be noted in the infant's clinical record.
- The research team at each site will consist of the local lead and a number of additional data collectors who have undergone training. These individuals will review whether or not these neonates meet the eligibility criteria, and approach the birthing parent to discuss the study if eligible
- Study data will be collected in participants where all eligibility criteria are met

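### The safeguard against changed testing behaviour names only local leads, yet the trained data collectors, all direct-care resident doctors, must also know the objectives and are not covered by it

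*Protocol*

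**What the plan says.** Section 5.3 of the protocol recognises the problem: "we appreciate that the presence of an ongoing study may change healthcare worker behaviour". Its mitigation has two parts in one sentence: "the full details of the study will only be discussed with local study leads, who will not be the healthcare workers identifying patients" for jaundice investigation on data collection days. Both the limit on information and the bar on identifying infants refer to local leads.

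Section 8 (study processes during prospective data collection) describes a wider team. Besides the lead, each site has "a number of additional data collectors who have undergone training, all of whom are paediatric resident doctors as part of the direct care team". These collectors are trained in the skin tone tool and "will have attended a training session on study processes".

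Section 9 (screening and recruitment) says of the lead and the collectors together: "These individuals will review whether or not these neonates meet the eligibility criteria, and approach the birthing parent to discuss the study if eligible". Section 9 (opt-out consent) sets what parents are told: "A verbal and written explanation of the study will be provided, explaining the study objectives, procedures, risks, and benefits". On collection days, "staff members carrying out jaundice assessments in relevant inpatient areas will be notified" and asked to alert the research team when a first test is under way.

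**The concern.** Objective 1 asks whether darker-skinned neonates are first tested only once their bilirubin is higher. The decision to test is thus the thing being studied, and a clinician who knows the question may decide differently. Section 5.3 relies on keeping full details away from anyone who might start a test. If several doctors in the direct care team hold the same knowledge and are outside the rule, the safeguard cannot work as written. A lower threshold for testing darker-skinned infants on collection days would pull the result towards no disparity, which is the falsely reassuring direction.

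**Working it through.** The point concerns conduct, so there is no planned figure to reproduce. The check sets the sections side by side and then asks which endpoints could move.

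**1. Who knows the objectives?** Section 5.3 says leads only. Section 9 has leads and collectors discussing the study with parents, and the explanation must include the objectives. Whoever explains the objectives knows them, so the collectors know them. Section 5.3 conflicts with Sections 8 and 9.

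**2. Who is barred from identifying infants for testing?** Section 5.3 names leads. Nothing in Sections 8, 9 or 11 extends the bar to collectors, who are "all of whom are paediatric resident doctors as part of the direct care team".

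**3. What limits their influence?**
- Sections 8 and 9 assign flagging to postnatal-area staff.
- Section 7 says bilirubin is measured mainly by midwives.
- Section 11 says training will stress that the total number of tests should not increase. This covers the count, not which infants are tested or when; the total can stay fixed while testing shifts between skin tones.

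**4. Which results could move?** The planning model in Section 10.1 has slope 2.6 µmol/L per hour of age. Write it as B = c + 2.6 × age + t, where t is the skin-tone effect. Section 10.2 puts age at measurement in every model except Bland-Altman.

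- *Earlier testing alone.* If a test is brought forward by h hours, age falls by h and B falls by 2.6 × h. Then B − 2.6 × age is unchanged, so the age-adjusted tone contrast does not move. The unadjusted level and the age at first measurement do; both are primary endpoints in Section 6.3. For scale, the target differences of 10, 20 and 30 µmol/L correspond to shifts in a group's mean testing age of 10/2.6 = 3.8 h, 20/2.6 = 7.7 h and 30/2.6 = 11.5 h. These are conversions, not predicted effects.
- *Lower threshold at a given age.* If a share p of a darker group is tested at a level lower by d at the same age, that group's adjusted contrast with tone 1 falls by p × d. Age adjustment does not remove this. The protocol gives no basis for p or d, so no size can be stated.

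**5. Could it be detected afterwards?** Table 1 and its footnotes record the indication (including whether a parent or a professional noticed jaundice) and the role of the person who took each measurement. These allow a partial check. Neither shows whether a study-team member prompted the test: a midwife can measure at a collector's request, and the indication would still read as noticed by a professional.

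**The case against.** The strongest reply is that the collectors' study role starts after the decision to test. Ward staff alert them when a first measurement is already under way, ward staff are not given full details, and no text asks a collector to start a test. Selective prompting by skin tone is an inference. The indication and staff-role fields give some means of looking for it, and the message about test numbers is a second safeguard. One could also read full details as meaning more than the objectives.

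Most of this stands, and it is why the likely influence is limited. It does not resolve the conflict. The objectives name the skin-tone comparison, so the narrower reading of full details still leaves collectors aware of the question. They remain direct-care doctors outside the one rule written to separate awareness from identification.

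A reader might go further and multiply assumed hours of earlier testing by 2.6 µmol/L per hour to claim that the Objective 1 contrast shrinks by that amount. The documents do not support this: the planned model includes age, and a shift along the age line cancels. Nor do they support saying that nothing restrains collectors or that no check is possible, given the assignment of flagging, the training message and the fields in Table 1.

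**Conclusion.** The inconsistency is real and should be corrected. The Section 5.3 safeguard cannot operate as stated, because Sections 8 and 9 require people other than leads to know and explain the objectives, and the bar on identifying infants does not reach them. Two routes to bias remain, both of unknown size:
- a changed testing threshold at a given age, which could shrink the age-adjusted Objective 1 contrast;
- a change in timing, which could move the age endpoint and the unadjusted level only.

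That aware doctors would prompt tests is an assumption; the protocol does not say that they will. The statement that age adjustment absorbs a pure time shift assumes bilirubin is linear in age with a common slope, as in the planning model. The case for changing the text rests on the sponsor having named this risk itself and on the low cost of the remedy, not on any computed bias.

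**What to change.** - Reconcile Section 5.3 with Sections 8 and 9: state that trained data collectors know the objectives, and extend the safeguard to all of them in their study role on collection days. Say expressly that this neither restricts nor delays clinically indicated tests.
- Add one yes/no field to the CRF: first test requested or prompted by a study-team member.
- Add a sensitivity analysis of Objective 1 that excludes infants with a yes. This is a check on robustness, not a corrected estimate, because removing those infants also changes who is analysed.

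The cost is protocol wording, one field, one further analysis and some attention to who collects data on a given day. Section 17 budgets £0 for staff, so the wording should be workable with the doctors already on the team.
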